### **3 STUDY OBJECTIVES**

#### **3.1 Primary Objective**

The primary objective is to compare gestational age-based dosing to standard dosing of unfractionated heparin for thromboprophylaxis of pregnant patients with prolonged hospitalizations and determine its effect on receipt of neuraxial anesthesia and pregnancy outcomes.

#### **3.2 Secondary Objectives**

The secondary objective of this study is to evaluate pharmacokinetics and pharmacodynamics of unfractionated heparin in pregnancy.

- a) Determine the frequency of adjusted unfractionated heparin dosing based on elevated aPTT values and assess maternal characteristics associated with elevated aPTT values.
- b) Determine the appropriate dosing of unfractionated heparin for pharmacologic thromboprophylaxis of hospitalized antepartum patients (anti-Xa levels within prophylactic goal range, normal aPTT).

## **4 STUDY DESIGN**

### **4.1 Study Overview**

This is a single center, open-label, non-placebo-controlled, randomized trial of gestational age-based dosing and standard dosing of unfractionated heparin for pharmacologic thromboprophylaxis of antepartum patients hospitalized for at least 72 hours. 46 (23 in arm 1 and 23 in arm 2) subjects are planned.

Screening data will be reviewed to determine subject eligibility. Subjects who meet all inclusion criteria and none of the exclusion criteria will be recruited for the study. Each subject will be assigned to receive one of two dosing of unfractionated heparin. Subjects will be assigned to the doses in random order.

The following treatment regimens will be used:

- ARM 1 (Control Arm)
  - o Standard dosing: 5,000 units subcutaneous unfractionated heparin every 12 hours
- ARM 2
  - o Gestational age-based dosing:
    - 1st trimester (< 14 weeks of gestation): 5,000 units subcutaneous unfractionated heparin every 12 hours
    - 2nd trimester (14-28 weeks of gestation): 7,500 units subcutaneous unfractionated heparin every 12 hours
    - 3rd trimester ( $\geq$  28 weeks of gestation): 10,000 units subcutaneous unfractionated heparin every 12 hours

Patients will receive serial lab measurements after 2nd dose, 4th dose, 10th dose, and then weekly to monitor. Dosing will be adjusted based on aPTT values (APPENDIX 1).

Total duration of subject participation will be throughout the patient's inpatient hospitalization until they undergo delivery or discharge. Total duration of the study is anticipated to be approximately 18 months.

## **5 CRITERIA FOR EVALUATION**

### **5.1 Primary Efficacy Endpoint**

- Elevated serum aPTT value above the normal range ( $> 36.2$  seconds). Prophylactic dosing of anticoagulation should not cause elevations in coagulation parameters.
  - o To be assessed after 2nd dose, 4th dose, and then weekly while receiving unfractionated heparin
  - o Surrogate marker for whether or not the patient would be eligible for neuraxial anesthesia based on guidelines for neuraxial anesthesia in pregnant women receiving VTE prophylaxis

- American Society for Regional Anesthesia (ASRA)
  - 5,000 units every 12 hours – normal aPTT value or 4 hours since last dose
  - 7,500 – 10,000 units every 12 hours – normal aPTT value and 12 ours since last dose
- Society of Obstetric Anesthesia and Perinatology
  - 5,000 units every 12 hours – always eligible for neuraxial anesthesia
  - 7,500 – 10,000 units every 12 hours – normal aPTT value or 12 hours since last dose

## 5.2 Secondary Efficacy Endpoints

- Diagnosis of venous thromboembolism (pulmonary embolism and/or deep venous thromboembolism)
- Nonreceipt or delay of neuraxial anesthesia due to unfractionated heparin defined as inability to receive neuraxial anesthesia due to an elevated aPTT value or because the subject received heparin
- Receipt of general anesthesia due to unfractionated heparin
- Delay in timing of delivery due to unfractionated heparin defined as presence of an indication to proceed with delivery via cesarean delivery or induction of labor but this does not immediately occur due to an elevated aPTT value or because the subject received heparin
- Mode of delivery
- Estimated blood loss at time of delivery
- Receipt of blood transfusion
- CBC for hemoglobin and platelet count (to be assessed weekly while receiving unfractionated heparin)
- Anti-Xa levels (to be assessed with aPTTs while receiving unfractionated heparin)
- Goal anti-Xa level achieved (0.2-0.5 IU/mL)
- Number of times adjustment in dose made
- Development of side effects from heparin administration (e.g bruising, epistaxis)
- Neonatal outcomes
  - Gestational age at delivery
  - Birthweight
  - 1 minute and 5 minute APGAR scores
  - Cord blood gas values: umbilical artery pH, umbilical artery CO2, umbilical artery base excess
  - NICU admission
  - Neonatal death

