Increasing dosing of heparin for thromboprophylaxis presents challenges in anesthetic management. Various anesthesia professional organizations have provided recommendations on when to proceed with neuraxial anesthesia for a patient on pharmacologic thromboprophylaxis, based on dose and time of administration and pertinent laboratory values such as activated partial thromboplastin time (aPTT). At our institution, neuraxial anesthesia can be offered at anytime if a patient is receiving 5,000 units SC every 12 hours, but if the patient is receiving 7,500 units-10,000 units SC every 12 hours then the anesthesiologists require at least a 6-12 hour interval with an aPTT value in the normal range ( $\leq 36.2$  seconds) to consider neuraxial anesthesia.

In an effort to decrease incidence of VTE and associated maternal morbidity and mortality, our institution has adopted the recommendations for pharmacologic thromboprophylaxis for all inpatient antepartum admissions over 72 hours and utilized ACOG's gestational age-based dosing for unfractionated heparin. An informal/pilot review of 30 antepartum admissions receiving trimester based dosing of unfractionated heparin for VTE prophylaxis demonstrated that 40% of the patients had an abnormally elevated aPTT value with two patients being in the therapeutic range. One patient was unable to receive an epidural in active labor and one patient had a delay in her cesarean delivery due to receiving heparin prophylaxis within the 6 hour interval. Although increased administration pharmacologic prophylaxis is associated with a decreased risk of VTE, our preliminary data demonstrates that the trimester based dosing of unfractionated heparin may lead to elevated aPTT values, potentially limiting the receipt of neuraxial anesthesia. This may then lead to an increased need for general anesthesia associated with both increased maternal and fetal risks.

To the best of our knowledge, there have been no prior studies comparing standard dosing with gestational age-based dosing of unfractionated heparin for VTE prophylaxis. The potential effects of higher prophylactic unfractionated heparin dosing need to be further explored before being widely adopted for inpatient antepartum thromboprophylaxis.

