### **8.2 Blinding**

Due to the objectives of the study, the identity of dosing will be known to investigators, medical providers, and patients. This study is non-blinded.

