**C. Stopping rules**

This study will be stopped prior to its completion if:

1. Gestational age-based dosing is associated with a significantly higher rate (defined as 50% of the study arm) of administration of general anesthesia despite dosing adjustments based on aPTT levels.
2. National guidelines from ACOG change during the trial and state that gestational age-based dosing should not be given for our study population.

3. Maternal or neonatal death occur secondarily to administration of unfractionated heparin.

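### The anaesthesia endpoints count only events attributed to heparin, so actual receipt of neuraxial or general anaesthesia, which the primary objective asks about, is not compared between arms

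*Protocol*

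**What the plan says.** **Objective.** Protocol 3.1, like the synopsis, aims to "determine its effect on receipt of neuraxial anesthesia and pregnancy outcomes". Nothing there restricts this to events caused by heparin.

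**Primary endpoint.** Section 5.1 uses a raised aPTT, described as a "Surrogate marker for whether or not the patient would be eligible for neuraxial anesthesia". It measures eligibility, not receipt.

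**Anaesthesia endpoints.** Section 5.2 lists two. The first combines nonreceipt with delay of neuraxial anaesthesia and is defined as "inability to receive neuraxial anesthesia due to an elevated aPTT value or because the subject received heparin". The second is "Receipt of general anesthesia due to unfractionated heparin", with no further definition.

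**Conditions of assessment.** Under 8.2, "the identity of dosing will be known to investigators, medical providers, and patients". No blinded or independent adjudication of cause is described. Under the site policy in 1.1, "neuraxial anesthesia can be offered at anytime if a patient is receiving 5,000 units SC every 12 hours", whereas at 7,500-10,000 units "the anesthesiologists require at least a 6-12 hour interval with an aPTT value in the normal range".

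**Analysis.** Protocol 11.3 and 11.4 and the SAP add no comparison of neuraxial or general anaesthesia regardless of cause. Mode of delivery is compared, but it is not an anaesthesia outcome. General anaesthesia appears without an explicit heparin qualifier only in the first stopping rule (Appendix 3, III.C), which speaks of a rate "of administration of general anesthesia despite dosing adjustments based on aPTT levels".

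**The concern.** Randomisation protects a comparison of who received neuraxial anaesthesia. It does not protect a judgement, made with knowledge of the dose, of why someone did not. The policy in 1.1 offers a ready heparin explanation in arm 2 from 14 weeks and much less of one in arm 1. Two women with the same course in labour could be classified differently because of their arm.

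Nor can receipt be recovered from the listed endpoint. A woman who waits and then has her epidural may count as an event through delay. A woman who never has one for another recorded reason does not count.

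At stake is the answer to the stated objective. The trial could report a difference in heparin-attributed events without showing whether the proportion of women who received neuraxial or general anaesthesia differed.

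**Working it through.** **1. The plan's own figure.** Inputs from 11.5: 40% v 3%, 80% power, alpha 0.05 (two-sided assumed), 1:1. With pooled variance, p̄ = 0.215:

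n = [1.96·√(2·0.215·0.785) + 0.8416·√(0.40·0.60 + 0.03·0.97)]² / 0.37² = (1.139 + 0.437)² / 0.1369 ≈ 18.1

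This rounds up to 19 per arm, against 18 stated; power at 18 is 79.7%. Then 18 × 1.25 = 22.5, so 23 per arm and 46 in total. The figure reproduces. It rests on aPTT only, so nothing below alters it.

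**2. Objective against endpoints.**

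| Question | Measured? | Compared by arm? |
|---|---|---|
| Eligibility for neuraxial (aPTT surrogate) | Yes, 5.1 | Yes, 11.3 |
| Neuraxial missed or delayed, attributed to heparin | Yes, 5.2 | Yes, 11.4 |
| General anaesthesia, attributed to heparin | Yes, 5.2, cause undefined | Yes, 11.4 |
| Neuraxial received, any reason | Not an endpoint | No |
| General anaesthesia received, any reason | Stopping rule at most | No |

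**3. What attribution can do (hypothetical counts, not from the documents).** Suppose 4 of 23 women in each arm miss neuraxial anaesthesia, and 3 of the 4 in arm 2 but none in arm 1 are put down to heparin.

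- Listed endpoint, ignoring delay: 3/23 v 0/23. Two-sided Fisher p = 2 × C(23,3)/C(46,3) = 2 × 1,771/15,180 = 0.23.
- Actual receipt: 19/23 v 19/23, difference 0. The simple 95% CI is ±1.96·√(2 × 0.826 × 0.174/23) = ±0.22.

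So the two definitions can disagree. The example is not a significant false result, and it says nothing about how likely such coding is.

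**4. What 46 women can show.** With 0 events in arm 1, two-sided Fisher at 0.05 needs at least 5/23 in arm 2: 2 × C(23,5)/C(46,5) = 0.049, whereas 4/23 gives 0.11. The pilot review in 1.1 reports one woman of 30 unable to have an epidural and one with a delayed cesarean.

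- Attributed events at 1/30 to 2/30 in arm 2 and none in arm 1: power 0.1% to 1.6% at 23 per arm.
- Any-reason events, with an assumed arm 1 rate of 5% to 20%: power 1% to 5% for a rise of 3.3 to 6.7 points, and 22% to 37% for a rise of 20 points.

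Neither version supports a confirmatory test. An added comparison would be descriptive.

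**The case against.** The strongest reply is that the site policy is part of the regimen. A woman refused neuraxial anaesthesia because she is within the waiting interval on 10,000 units was refused because of her dose, and that is the effect the rationale in section 2 sets out to study. This stands. A reader might infer that the attributed contrast merely follows the arm label and is all bias. The documents do not support that: part of any difference may be real. But a real loss of receipt would also appear in an any-reason comparison, so the reply does not remove the need for one.

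The neuraxial definition is also partly anchored. aPTT is a laboratory value, and 8.7 takes the dose and time of heparin from the administration record. This stands too, and narrows the concern to borderline cases. It does not help the general anaesthesia endpoint, which has no definition.

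A reader might expect no attributed events in arm 1 whatever happens there. That goes too far. Section 5.1 also cites guidance that sets conditions at 5,000 units, and the plan's own 3% implies 0.03 × 23 = 0.69 women in arm 1 with a raised aPTT. The arms are not cleanly separated either: first-trimester women in arm 2 receive 5,000 units (4.1), and doses are lowered for a raised aPTT (8.4.1).

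A reader might also take the stopping rule as proof that any-cause general anaesthesia is already needed. Its wording does not say so and can be read as heparin-related.

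**Conclusion.** The concern holds as a gap in the endpoints. The objective names receipt of neuraxial anaesthesia, and no planned analysis compares receipt of neuraxial or general anaesthesia by arm. What is compared is the aPTT surrogate and events attributed to heparin. The attributed contrast combines the regimen's real effect with possible differential attribution, and the plan gives no means of separating them.

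It would be too strong to say that the objective goes untested, because section 2 ties it to aPTT as a surrogate and 11.3 tests that.

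The conclusion rests on one inference. The documents do not say who assigns cause; that it is someone aware of the dose follows from 8.2 and the absence of any adjudication procedure. The size of any misattribution is unknown, and the 3 v 0 illustration is an assumption. The sample size and the primary analysis are unaffected.

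**What to change.** In Protocol 5.2 and the SAP, add two endpoints, each compared by randomised arm:

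- receipt of neuraxial anaesthesia for delivery (yes/no, any reason);
- receipt of general anaesthesia for delivery (yes/no, any reason).

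State the denominator. Participation can end at discharge (4.1), so it should be women with an on-study delivery, with that number shown per arm because the subset is formed after randomisation. Report each result as a difference in proportions with a 95% CI, by a method suited to small counts, and present it as descriptive.

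Keep the existing nonreceipt-or-delay and heparin-attributed endpoints alongside, so that delay is not lost, and tabulate the recorded reasons by arm. Define what counts as caused by heparin for general anaesthesia.

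**Cost.** Two yes/no items from the anaesthesia record and a few lines of text. The case report form items listed in 15.1 do not include anaesthesia, so collection should be specified. The SAP is written in the past tense; if the analysis has been done, the results should be labelled as added afterwards. The downside is that any-reason rates include causes unrelated to heparin and are less specific, which is why the attributed endpoints stay.

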## 6 SUBJECT SELECTION

### 6.1 Study Population

Subjects that are pregnant and undergoing antepartum admission for at least 72 hours who meet the inclusion and exclusion criteria will be eligible for participation in this study.

## **6.2 Inclusion Criteria**

1. Female  $\geq$  18 years of age at Visit X.
2. Antepartum admission for at least 72 hours at Ronald Reagan UCLA Medical Center
3. Speaks English or Spanish
4. Written informed consent (and assent when applicable) obtained from subject or subject's legal representative and ability for subject to comply with the requirements of the study.

## **6.3 Exclusion Criteria**

1. Active or threatened antenatal bleeding
2. Risk of imminent delivery (delivery within 12 hours)
3. Disseminated intravascular coagulation
4. Thrombocytopenia (platelet count  $< 100 \times 10^9$ )
5. Elevated baseline aPTT ( $> 36.2$  seconds)
6. Concern for hemolysis, elevated liver enzymes, low platelet count (HELLP) syndrome
7. Congenital bleeding disorders (e.g., hemophilias)
8. Receiving therapeutic or prophylactic anticoagulation (unfractionated heparin, low molecular weight heparin, oral anticoagulants) for alternative indications (e.g., acquired or inherited thrombophilia, history of VTE)
9. History of heparin-induced thrombocytopenia (HIT)
10. SARS-CoV-2 positive
11. Cognitive impairment, psychiatric instability, or language barriers that limit their ability to provide informed consent
12. Presence of a condition or abnormality that in the opinion of the Investigator would compromise the safety of the patient or the quality of the data.

## **7 CONCURRENT MEDICATIONS**

### **7.1 Allowed Medications and Treatments**

Standard therapy provided in pregnancy is allowed except for treatments noted in the exclusion criteria described above and as noted in the prohibited medications section below.

### **Prohibited Medications and Treatments**

The following medications are prohibited during the study and administration will be considered a protocol violation.

- Low molecular weight heparin
- Oral anticoagulants

## **8 STUDY TREATMENTS**

### **8.1 Method of Assigning Subjects to Treatment Groups**

46 eligible patients will be randomly assigned to standard dosing of unfractionated heparin or gestational age-based dosing of unfractionated heparin in a 1:1 ratio. They will immediately be allocated to their designated arm and this will be documented in their prenatal record. The medical team will be notified of the patient's designated arm and then place the order for unfractionated heparin.

### **8.2 Blinding**

Due to the objectives of the study, the identity of dosing will be known to investigators, medical providers, and patients. This study is non-blinded.

### **8.3 Formulation of Test and Control Products**

The drug product to be studied is unfractionated heparin, which is a previously standardized medication. Formulation will be per UCLA pharmacy.

#### **8.3.1 Formulation of Test Product**

The tested product will be two variations in dosing of unfractionated heparin. Formulation and dispensing of medication will be per UCLA pharmacy after the appropriate order with assigned dosing is placed by the medical team.

#### **8.3.2 Formulation of Control Product**

No control product will be provided.

#### **8.3.3 Packaging and Labeling**

Not applicable.

### **8.4 Supply of Study Drug at the Site**

Unfractionated heparin will be provided by the UCLA pharmacy.

#### **8.4.1 Dosage/Dosage Regimen**

ARM 1: Standard dosing

- Dose: 5,000 units unfractionated heparin subcutaneous injection every 12 hours
- Decrease in dosing will be made for elevated aPTT > 36.2 seconds (APPENDIX 1)

ARM 2: Gestational age-based dosing

- Dose:
  - o If less than 14 weeks of gestation - 5,000 units unfractionated heparin subcutaneous injection every 12 hours
  - o If 14 weeks of gestation to 27 and 6 weeks of gestation – 7,500 units unfractionated heparin subcutaneous injection every 12 hours
  - o If greater than or equal to 28 weeks of gestation – 10,000 units unfractionated heparin subcutaneous injection every 12 hours

- Decrease in dosing will be made for elevated aPTT > 36.2 seconds (APPENDIX 1)

#### **8.4.2 Dispensing**

The pharmacist will dispense the drug.

#### **8.4.3 Administration Instructions**

The assigned inpatient nurse caring for the patient will administer the drug.

### **8.5 Supply of Study Drug at the Site**

Not applicable since this is not a study drug.

#### **8.5.1 Storage**

Unfractionated heparin will be stored in the pharmacy per UCLA pharmacy protocol.

### **8.6 Study Drug Accountability**

Not applicable since this is not a study drug.

### **8.7 Measures of Treatment Compliance**

Treatment compliance will be ensured through study staff's evaluation of the patient's medication administration record (MAR) in the medical chart. This provides information on dose provided and time of administration.

## **9 STUDY PROCEDURES AND GUIDELINES**

A Schedule of Events representing the required testing procedures and adjustments in dosing of medications to be performed for the duration of the study is diagrammed in Appendix 1.

Prior to conducting any study-related activities, written informed consent and the Health Insurance Portability and Accountability Act (HIPAA) authorization must be signed and dated by the subject or subject's legal representative. If appropriate, assent must also be obtained prior to conducting any study-related activities.

### **9.1 Clinical Assessments**

#### **9.1.1 Concomitant Medications**

All concomitant medication and concurrent therapies will be documented at screening. Dose, route, unit frequency of administration, and indication for administration and dates of medication will be captured.

#### **9.1.2 Demographics**

Demographic information (date of birth, gender, race) will be recorded at screening.

#### **9.1.3 Medical History**

Relevant medical history, including history of current disease, other pertinent respiratory history, and information regarding underlying diseases will be recorded at screening.

#### **9.1.4 Physical Examination**

A complete physical examination will be performed by the medical team, which consists of a physician at UCLA Medical Center, on admission to the hospital. This physical exam will be documented in the medical chart. The medical team (MD, RN) will perform physical exams daily per hospital protocol and monitor for development of side effects (e.g., bruising, rash, epistaxis). New abnormal physical exam findings must be documented and will be followed by a physician once reported.

#### **9.1.5 Vital Signs**

Body temperature, blood pressure, pulse and respirations will be performed after resting for 5 minutes at least once daily as part of the patient's hospitalization.

#### **9.1.6 Adverse Events**

Information regarding occurrence of adverse events will be captured throughout the study. Duration (start and stop dates and times), outcome, treatment and relation to study drug will be recorded on the case report form (CRF).

### **9.2 Clinical Laboratory Measurements**

#### **9.2.1 Hematology**

Blood will be obtained and sent to the clinical hematology lab for a complete blood count (hemoglobin, hematocrit, red blood cell count, white blood cell count, white blood cell differential, and platelet count), activated partial thromboplastin time (aPTT), and anti-Xa levels.

#### **9.2.2 Blood Chemistry Profile**

Blood will be obtained and sent to each clinical chemistry lab for determination of creatinine.

## **10 EVALUATIONS BY VISIT**

REFER TO APPENDIX 2

### **10.1 Visit 1: Day 1**

1. Review the study with the subject (subject's legal representative) and obtain written informed consent and HIPAA authorization and assent, if appropriate.
2. Assign the subject a unique screening number.
3. Record demographics data.
4. Record medical and surgical history
5. Record concomitant medications.
6. Collect blood for clinical laboratory tests (CBC, aPTT, anti-Xa, serum creatinine).
7. Randomize subject
8. Order unfractionated heparin dosing that subject is randomized to (first dose ordered for 21:00 PM the day patient is randomized)

